7.2.2. Subject Electronic Diary

The subject will be asked to monitor and record local reactions, systemic events, fever, and antipyretic/pain medication used to treat symptoms, each evening for 14 days following vaccination (Day 1 through Day 14, where Day 1 is the day of vaccination) on a system that uses a personal digital assistant (PDA) or other technology. This system, hereafter referred to as the subject's e-diary, allows recording of these assessments only within a fixed time window, thus providing the accurate representation of the subject's experience at that time. Data on local reactions, systemic events, fever, and antipyretic/pain medication used to treat symptoms reported on the e-diary will be transferred electronically to the e-diary vendor, where they will be available for review by investigators, their appropriately qualified designees, and sponsor staff at all times via an internet-based portal. At intervals agreed to by the vendor and Pfizer, these data will be transferred electronically to Pfizer for analysis and reporting.

These data do not need to be reported by the investigator in the CRF. However, if a subject withdraws because of prompted events reported in the e-diary, the event(s) should be recorded on the AE page of the CRF, regardless of whether the investigator considers the event(s) to be clinically significant.

Investigators (or appropriately qualified designees) are required to review the e-diary data online at frequent intervals (daily is optimal) to evaluate subject compliance and as part of the ongoing safety review (see Stopping Rules in [Section 7.2.1](#)).

The investigator or designee must contact the subject in order to obtain stop dates for any reactions ongoing on the last day that the e-diary was completed. The stop dates should be entered in the CRF at Visit 2.

7.2.3. Grading Scale for Prompted Events

The grading scales used in this study to assess AEs as described below are based on concepts outlined in the Food and Drug Administration (FDA) Center for Biologics Evaluation and Research (CBER) guidelines on toxicity grading scales for healthy adult volunteers enrolled in preventive vaccine clinical trials.⁶¹

7.2.3.1. Local Reactions

From Day 1 to Day 14, where Day 1 is the day of vaccination, subjects will be asked to assess redness, swelling, and pain at the injection site and to record the symptoms in the e-diary in the evening. Redness and swelling will be measured and recorded in measuring device units (range: 1 to 21+), and then categorized during analysis as mild, moderate, or severe based on the grading scale in [Table 1](#) below. Measuring device units can be converted to centimeters according to the following scale: 1 measuring device unit = 0.5 cm. Pain at the vaccine injection site will be assessed by the subject as mild, moderate, or severe according to the grading scale in [Table 1](#). A subject with a severe (Grade 3 or above) local reaction will be prompted to contact the investigator to assess the reaction and perform an unscheduled assessment or visit as appropriate.

Only an investigator is able to classify a subject's local reaction as Grade 4, after physical examination of the subject or documentation from another medically qualified source (eg, emergency room or hospital record) or, in the case of pain at the injection site only, telephone contact with the subject. If a subject experiences a Grade 4 local reaction, the investigator must immediately notify the sponsor. Site staff will educate the subject regarding signs and symptoms that would prompt site contact.

The procedure for notification of the sponsor is provided in the study reference manual (SRM) or equivalent.

Table 1. Grading Scales for Local Reactions

	Mild Grade 1	Moderate Grade 2	Severe Grade 3^a	Grade 4^b
Redness (synonym with erythema)	5 to 10 measuring device units = 2.5 to 5.0 cm	11 to 20 measuring device units = 5.5 to 10.0 cm	≥21 measuring device units = ≥10.5 cm	Necrosis or exfoliative dermatitis
Swelling (synonym with edema)	5 to 10 measuring device units = 2.5 to 5.0 cm	11 to 20 measuring device units = 5.5 to 10.0 cm	≥21 measuring device units = ≥10.5 cm	Necrosis
Pain at injection site	Does not interfere with activity	Interferes with activity	Prevents daily activity ^c	Emergency room visit or hospitalization

Abbreviations: CRF = case report form; e-diary = electronic diary.

Note: If the size of the redness and/or swelling falls between 2 measuring device units, the higher measuring device unit number will be recorded in the e-diary.

- Subjects experiencing Grade 3 local reactions will be asked to contact the study site. In the event that the subject does not call, the investigator will call the subject.
- Grade 4 assessment should be made by the investigator. Grade 4 will not be collected in the e-diary but will be collected as an AE on the CRF. The severity of the local reaction should be graded using the AE severity grading scale in [Section 8.3](#).
- Prevents daily activity, ie, results in missed days of work or school or is otherwise incapacitating.

7.2.3.2. Systemic Events

From Day 1 to Day 14, where Day 1 is the day of vaccination, subjects will be asked to assess headache, fatigue, muscle pain, and joint pain and to record the symptoms in the e-diary in the evening. The symptoms will be assessed by the subject as mild, moderate, or severe according to the grading scale in [Table 2](#) below. Subjects will also be instructed to contact site staff if they experience any possible Grade 4 prompted systemic event (ie, emergency room visit or hospitalization for headache, fatigue, muscle pain, or joint pain) within 14 days after vaccination. Study staff may also contact the subject to obtain additional information on Grade 3 events entered into the e-diary.

Only an investigator is able to classify a subject's systemic event as Grade 4, after physical examination of the subject or documentation from another medically qualified source

(eg, emergency room or hospital record) or telephone contact with the subject. If a subject experiences a Grade 4 systemic event, the investigator must immediately notify the sponsor.

The procedure for notification of the sponsor is provided in the SRM or equivalent.

Table 2. Grading Scales for Systemic Events

	Mild Grade 1	Moderate Grade 2	Severe Grade 3^a	Grade 4^b
Fatigue (synonym with tiredness)	Does not interfere with activity	Some interference with activity	Prevents daily routine activity	Emergency room visit or hospitalization
Headache	Does not interfere with activity	Some interference with activity	Prevents daily routine activity	Emergency room visit or hospitalization
Muscle pain	Does not interfere with activity	Some interference with activity	Prevents daily routine activity	Emergency room visit or hospitalization
Joint pain	Does not interfere with activity	Some interference with activity	Prevents daily routine activity	Emergency room visit or hospitalization

Abbreviations: CRF = case report form; e-diary = electronic diary.

- a. Prevents daily routine activity, ie, results in missed days of work or school or is otherwise incapacitating.
- b. Grade 4 assessment should be made by the investigator; Grade 4 will not be collected in the e-diary but will be collected as an AE on the CRF. The severity of the systemic event should be graded using the AE severity grading scale in [Section 8.3](#).

7.2.3.3. Fever

In order to record information on fever, a digital thermometer will be given to the subject with instructions on how to measure oral temperature at home. Temperature will be collected in the evening daily for 14 days following vaccination (Days 1 to 14, where Day 1 is the day of vaccination) and at any time during the 14 days that fever is suspected. Fever is defined as an oral temperature of $\geq 100.4^{\circ}\text{F}$ ($\geq 38.0^{\circ}\text{C}$). The highest temperature for each day will be recorded in the e-diary. In the event of a fever on Day 14, temperature will be collected daily until fever has resolved (1 day of temperature $< 100.4^{\circ}\text{F}$ [$< 38.0^{\circ}\text{C}$]) in order to collect a stop date in the CRF. A subject with a fever $> 104.0^{\circ}\text{F}$ ($> 40.0^{\circ}\text{C}$) will be prompted to contact the investigator to assess the fever and perform an unscheduled assessment or visit as appropriate. Study staff may also contact the subject to obtain additional information if a temperature of $> 102^{\circ}\text{F}$ is entered into an e-diary. Temperature will be measured and recorded to 1 decimal place and then grouped into ranges for the analysis according to Table 3 below.

Table 3. Ranges for Fever

100.4°F to 101.1°F (38.0°C to 38.4°C)
101.2°F to 102.0°F (38.5°C to 38.9°C)
102.1°F to 104.0°F (39.0°C to 40.0°C)
$> 104.0^{\circ}\text{F}$ ($> 40.0^{\circ}\text{C}$)

7.2.3.4. Use of Antipyretic/Pain Medication

From Day 1 to Day 14, where Day 1 is the day of vaccination, the subject will be asked to record the use of antipyretic and/or pain medication used to treat symptoms (yes/no) in the e-diary in the evening.

7.3. Immunogenicity

Blood samples (approximately 50 mL/visit) for immunogenicity assessments will be collected from all subjects prior to vaccination (Visit 1/Day 1), at Visit 2 approximately 1 month after vaccination, **CCI**

██████████. Serum samples should be processed and stored as indicated in the SRM.

The total volume of blood collected from each subject will be approximately 120 mL (Stage 1 subjects) or 150 mL (Stage 2 subjects) (~50 mL/visit). Sera will be used for immunogenicity assessments and assay development purposes.

OPA titers for the 7 pneumococcal serotypes (8, 10A, 11A, 12F, 15B, 22F, and 33F) will be determined in all subjects for each blood sample. Results will be reported as OPA titers.

CCI
██████████

Immunogenicity assays will be performed at Pfizer Vaccine Research & Development Laboratory located at [name] and/or at a facility designated by Pfizer.

7.4. Laboratory Tests: Stage 1 Only

The safety laboratory tests will be performed at times defined in the [Schedule of Activities](#) and [Section 6](#) of the protocol.

The FDA toxicity grading scale⁶¹ for healthy adult and adolescent volunteers enrolled in preventive vaccine clinical trials will be used to grade abnormalities.

If abnormal laboratory parameters are reported at screening **CCI** and the investigator believes the results to be erroneous or to represent stable Grade 1 abnormalities, the abnormal laboratory parameters may be retested. Subjects with stable Grade 1 abnormalities may be considered eligible at the discretion of the investigator. A “stable” Grade 1 laboratory abnormality is defined as a report of Grade 1 on an initial blood sample that remains ≤ Grade 1 upon repeat testing on a second sample from the same subject.

Hematology	Chemistry ^a
Hemoglobin	BUN/urea and creatinine
Hematocrit	AST, ALT
RBC count	Total bilirubin
Platelet count	Alkaline phosphatase
WBC count with differential	

Abbreviations: ALT = alanine aminotransferase; AST = aspartate aminotransferase; BUN = blood urea nitrogen; RBC = red blood cell; WBC = white blood cell.

a. Please refer to [Section 8.4.2](#) for additional testing required for subjects who meet Hy's law criteria.

7.5. Biological Samples

Blood samples will be used only for scientific research. Each sample will be labeled with a code so that the laboratory personnel testing the samples will not know the subject's identity. Samples that remain after performing assays outlined in the protocol may be stored by Pfizer. Unless a time limitation is required by local regulations or ethical requirements, the samples will be stored for up to 15 years after the end of the study and then destroyed. If allowed by the informed consent document, stored samples may be used for additional testing to better understand the immune responses to the vaccine(s) under study in this protocol, to inform the development of other products, and/or for vaccine-related assay work supporting vaccine programs. No testing of the subject's genetic material will be performed.

The subject may request that his or her samples, if still identifiable, be destroyed at any time; however, any data already collected from those samples will still be used for this research. The biological samples may be shared with other researchers as long as confidentiality is maintained and no testing of the subject's genetic material is performed.

8. ADVERSE EVENT REPORTING

8.1. Requirements

The table below summarizes the requirements for recording safety events on the CRF and for reporting safety events on the Clinical Trial (CT) SAE Report Form to Pfizer Safety. These requirements are delineated for 3 types of events: (1) SAEs; (2) nonserious AEs; and (3) exposure to the investigational product under study during pregnancy or breastfeeding, and occupational exposure.

Safety Event	Recorded on the CRF	Reported on the CT SAE Report Form to Pfizer Safety Within 24 Hours of Awareness
SAE	All	All
Nonserious AE ^a	All	None
Exposure to the investigational product under study during pregnancy or breastfeeding, and occupational exposure	All (regardless of whether associated with an AE), except occupational exposure	Exposure during pregnancy, exposure via breastfeeding, occupational exposure (regardless of whether associated with an AE)

a. Nonserious AEs will be recorded from the time the subject provides informed consent through and including Visit 2. After Visit 2, only NDCMCs (can be nonserious) and SAEs will be reported.

All observed or volunteered events regardless of vaccine group or suspected causal relationship to the investigational product(s) will be reported as described in the following paragraphs.

Events listed in the table above that require reporting to Pfizer Safety on the CT SAE Report Form within 24 hours of awareness of the event by the investigator **are to be reported regardless of whether the event is determined by the investigator to be related to an investigational product under study**. In particular, if the SAE is fatal or life-threatening, notification to Pfizer Safety must be made immediately, irrespective of the extent of available event information. This time frame also applies to additional new (follow-up) information on previously forwarded reports. In the rare situation that the investigator does not become immediately aware of the occurrence of an event, the investigator must report the event within 24 hours after learning of it and document the time of his/her first awareness of the event.

For each event, the investigator must pursue and obtain adequate information both to determine the outcome and to assess whether it meets the criteria for classification as an SAE (see the Serious Adverse Events section below). In addition, the investigator may be requested by Pfizer Safety to obtain specific follow-up information in an expedited fashion. This information is more detailed than that recorded on the CRF. In general, this will include a description of the event in sufficient detail to allow for a complete medical assessment of the case and independent determination of possible causality. Any information relevant to the event, such as concomitant medications and illnesses, must be provided. In the case of a subject death, a summary of available autopsy findings must be submitted as soon as possible to Pfizer Safety. Any pertinent additional information must be reported on the CT SAE Report Form; additional source documents (eg, medical records, CRF, laboratory data) are to be sent to Pfizer Safety **ONLY** upon request.

As part of ongoing safety reviews conducted by the sponsor, any nonserious AE that is determined by the sponsor to be serious will be reported by the sponsor as an SAE. To assist in the determination of case seriousness, further information may be requested from the investigator to provide clarity and understanding of the event in the context of the clinical study.

For Stage 1 subjects, the investigator must contact the Pfizer study physician directly as soon as possible after becoming aware of a nonprompted severe AE or SAE occurring within 14 days after vaccination. Additional information regarding such events and the reporting requirements can be found in the SRM or equivalent.

8.1.1. Additional Details on Recording Adverse Events on the CRF

All events detailed in the table above will be recorded on the AE page(s) of the CRF. It should be noted that the CT SAE Report Form for reporting of SAE information is not the same as the AE page of the CRF. When the same data are collected, the forms must be completed in a consistent manner. AEs should be recorded using concise medical terminology and the same AE term should be used on both the CRF and the CT SAE Report Form for reporting of SAE information.

8.1.2. Eliciting Adverse Event Information

The investigator is to record on the CRF all directly observed AEs and all AEs spontaneously reported by the study subject. In addition, each study subject will be questioned about the occurrence of AEs in a nonleading manner.

8.1.3. Withdrawal From the Study Due to Adverse Events (see also the Subject Withdrawal Section)

Withdrawal due to AEs should be distinguished from withdrawal due to other causes, according to the definition of AE noted below, and recorded on the CRF.

When a subject withdraws from the study because of an SAE, the SAE must be recorded on the CRF and reported, as appropriate, on the CT SAE Report Form, in accordance with the Requirements section above.

8.1.4. Time Period for Collecting AE/SAE Information

The time period for actively eliciting and collecting AEs, SAEs, and NDCMCs (“active collection period”) for each subject begins from the time the subject provides informed consent, which is obtained before the subject’s participation in the study (ie, before undergoing any study-related procedure and/or receiving investigational product), through and including Visit 2. Between Visit 2 and Visit 3 (Stage 1) and Visit 2 and Visit 4 (Stage 2), only NDCMCs and SAEs will be reported. An NDCMC is defined as a disease or medical condition, not previously identified, that is expected to be persistent or is otherwise long-lasting in its effects.

For subjects who are screen failures, the active collection period ends when screen failure status is determined.

8.1.4.1. Reporting SAEs to Pfizer Safety

All SAEs occurring in a subject during the active collection period are reported to Pfizer Safety on the CT SAE Report Form.

SAEs occurring in a subject after the active collection period has ended are reported to Pfizer Safety if the investigator becomes aware of them; at a minimum, all SAEs that the investigator believes have at least a reasonable possibility of being related to investigational product must be reported to Pfizer Safety.

Follow-up by the investigator continues throughout and after the active collection period and until the event or its sequelae resolve or stabilize at a level acceptable to the investigator, and Pfizer concurs with that assessment.

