 - Remind the subject that study staff may assess him or her to obtain additional information on Grade 3 events entered into the e-diary.
 - Ask the subject to contact the investigator or site staff immediately if any significant illness or medical event (eg, emergency room visit or hospitalization) occurs during the study period.
 - Remind the subject to use appropriate contraceptives until 28 days after vaccination, if applicable.

- Record AEs as described in [Section 8](#).
- The investigator or an authorized designee completes the CRF and updates the investigational product accountability records.
- The investigator or appropriately qualified designee reviews the e-diary data online at frequent intervals (daily is optimal) for the 14 days following vaccination to evaluate subject compliance and as part of the ongoing safety review.

6.1.3. Visit 2 (Month 1; 28 to 35 Days After Vaccination) – Clinic Visit

- Ensure and document that the subject continues to be eligible for the study and that none of the temporary blood draw delay criteria are met.
- Perform a contraception check (see [Section 4.4.1](#)), if applicable.
- Record nonstudy vaccinations and concomitant medications as described in [Section 5.11.3](#).
- **CC1** [REDACTED]
- Collect a blood sample of approximately 50 mL for immunogenicity assessments.
- Review the subject's e-diary data and collect the e-diary. Collect stop dates of any e-diary events ongoing on the last day that the e-diary was completed and record stop dates in the CRF.
- Determine whether any AEs, SAEs, or NDCMCs have occurred since Visit 1 and follow up on any previously reported ongoing AEs, SAEs, or NDCMCs to determine the outcome (ie, record stop dates or confirm if they are still continuing) and record as described in [Section 8](#).
- Remind the subject to contact the investigator or site staff immediately if any significant illness or medical event (eg, emergency room visit or hospitalization) occurs during the study period.
- The investigator or an authorized designee completes the CRF.

6.1.4. Visit 3 (Month 6; 168 to 196 Days After Vaccination) – Telephone Contact

- Record nonstudy vaccinations and medications as described in [Section 5.11.3](#).
- Determine whether any NDCMCs or SAEs have occurred since Visit 2 and follow up on any previously reported ongoing AEs, SAEs, or NDCMCs to determine the outcome (ie, record stop dates or confirm if they are still continuing) and record as described in [Section 8](#).

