8.1.4.2. Recording Nonserious AEs and SAEs on the CRF

During the active collection period, both nonserious AEs and SAEs are recorded on the CRF.

Follow-up by the investigator may be required until the event or its sequelae resolve or stabilize at a level acceptable to the investigator, and Pfizer concurs with that assessment.

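### The related-only floor for SAE reporting takes effect at Visit 2 instead of after the last visit, and Stage 2 subjects withdrawn by the investigator or sponsor have no specified 12-month safety contact

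*Protocol*

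**What the plan says.** **SAEs after Visit 2.** Protocol 8.1.4 runs one active collection period, covering AEs, SAEs and NDCMCs together, from consent "through and including Visit 2". Its next sentence adds: "Between Visit 2 and Visit 3 (Stage 1) and Visit 2 and Visit 4 (Stage 2), only NDCMCs and SAEs will be reported". Section 8.1.4.1 then deals with SAEs after the active period. Its opening clause has them reported to the sponsor's safety group if the investigator becomes aware of them. Its closing clause sets a floor: "at a minimum, all SAEs that the investigator believes have at least a reasonable possibility of being related to investigational product must be reported".

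Section 8.1 has all SAEs both recorded on the CRF and reported within 24 hours of awareness, "regardless of whether the event is determined by the investigator to be related to an investigational product under study". Footnote a of its table says: "After Visit 2, only NDCMCs (can be nonserious) and SAEs will be reported". Section 8.4.1 repeats that all SAEs are reported, with no causality limit. On the CRF, 8.1.1 says: "All events detailed in the table above will be recorded on the AE page(s) of the CRF", while 8.1.4.2 mentions only the active period: "During the active collection period, both nonserious AEs and SAEs are recorded on the CRF".

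Sites also question subjects after Visit 2. Protocol 6.1.4 (Stage 1, Month 6) instructs: "Determine whether any NDCMCs or SAEs have occurred since Visit 2". Section 6.2.3 repeats this for Stage 2, and 6.2.4 asks at Month 12 about the time since Visit 3.

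**Withdrawn subjects.** Protocol 6.4 specifies one safety telephone contact, at 6 months, for everyone withdrawn after vaccination, without distinguishing the stages. Section 6.4.1 keeps subjects who themselves ask to discontinue in protocol-specified follow-up, unless they withdraw consent for contact. Section 6.4.2 allows withdrawal by the investigator or sponsor. It asks for effort to document the subject's outcome, a final visit where applicable, and follow-up of unresolved AEs. The primary endpoint in 2.1.2 counts SAEs and NDCMCs to 12 months in Stage 2.

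**The concern.** A site handling an SAE in, say, month 4 that it judges unrelated finds two mandatory minimums. Section 8.1 makes the report compulsory. In 8.1.4.1 the compulsory wording attaches only to possibly related events. A related-only floor makes sense once a subject has finished the study. Here it starts at Visit 2, while subjects are still being questioned for a primary endpoint, because 8.1.4 gives SAEs the same end date as nonserious AEs.

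The second issue is that the only follow-up named for withdrawn subjects ends at Month 6, the last time point of Stage 1 but only halfway through Stage 2. Someone withdrawn because a new condition meets an exclusion criterion may well differ in SAE or NDCMC risk from those who stay, so the unobserved months may not be missing at random.

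**Working it through.** The plan gives no figure on this point to reproduce. The first check compares texts. The second and third are arithmetic.

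**1. Duty for an SAE after Visit 2 that is judged unrelated**

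| Place | What it requires |
|---|---|
| 8.1 table and text | Report and record, whatever the causality |
| 8.1 footnote a; 8.1.4, second sentence | SAEs still reported after Visit 2; no causality limit |
| 8.4.1 | All SAEs reported |
| 6.1.4, 6.2.3, 6.2.4 | Asked about at Visits 3 and 4; no causality limit |
| 8.1.4.1, opening clause | Reported on awareness; agrees with 8.1 |
| 8.1.4.1, closing clause | Outside the stated mandatory minimum |
| 8.1.4.2 | Silent after Visit 2; 8.1.1 fills the gap |

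Only the closing clause of 8.1.4.1 is out of line. It governs reports to the safety group, not CRF entry.

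**2. Time affected**

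The visit windows are Visit 2 at day 28 to 35, Visit 3 at day 168 to 196, and Visit 4 at day 350 to 378.

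- Share of the 6-month window after Visit 2: 1 − 35/168 = 0.79 to 1 − 28/196 = 0.86.
- Share of the 12-month window after Visit 2: 1 − 35/350 = 0.90 to 1 − 28/378 = 0.93.
- Stage 2 subject withdrawn at Visit 3: 350 − 196 = 154 to 378 − 168 = 210 days without a specified contact, which is 154/350 = 44% to 210/378 = 56% of the 12-month window.

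The first two lines show how long the ambiguous floor applies. They do not measure lost data.

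**3. Illustrative effect of the missing 12-month contact**

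The documents give neither an SAE rate nor a rate of investigator- or sponsor-initiated withdrawal, so all inputs are assumptions. They are a 12-month risk of 8% in other subjects, a fraction *f* of subjects affected, and a hazard ratio HR in those affected. Withdrawal is uniform over 12 months, with observation to Month 6 or to withdrawal, whichever is later.

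Let λ = −ln(0.92)/12. The true risk in affected subjects is R = 1 − 0.92^HR. The observed risk is O = 0.5·(1 − e^(−6·HR·λ)) + (1/12)·∫₆¹²(1 − e^(−HR·λ·t))dt.

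- HR 1: R = 0.0800, O = 0.0507.
- HR 3: R = 0.2213, O = 0.1440.

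*Partly followed subjects kept and counted event-free when no event was seen.* The understatement is f·(R − O):
- f = 1%, HR 1 to 3: 0.03 to 0.08 percentage points.
- f = 2%, HR 1 to 3: 0.06 to 0.155 points.
- f = 10%, HR 1 to 3: 0.29 to 0.77 points.

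*Affected subjects excluded.* The understatement is f·(R − 0.08). With f = 10%:
- HR 1: 0.
- HR 3: 0.10 × (0.2213 − 0.08) = 1.41 points.
- HR 0.5: R = 1 − 0.92^0.5 = 0.0408, so 0.10 × (0.0408 − 0.08) = −0.39 points, an overstatement.

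Both size and sign therefore depend on the denominator rule. SAP 5.1 lets subjects who lack safety data for an analysis be excluded from it, and does not say whether that covers partial follow-up.

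For scale, the planned Clopper-Pearson interval at 18/220 (8.2%) is 4.9% to 12.6%.

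**The case against.** **On the reporting floor.** The opening clause of 8.1.4.1 already has SAEs reported on awareness, and a minimum does not say that unrelated SAEs may be withheld. A site that follows 8.1 satisfies both passages, and the all-SAE rule is stated several times. This largely stands. A reader might infer that unrelated SAEs drop out of the 6- and 12-month endpoint. The documents do not support that: Visits 3 and 4 ask about every SAE, and 8.1 with 8.1.1 sends them all to the CRF. What survives is that the mandatory wording in 8.1.4.1 is weaker than in 8.1 for a period in which 8.1 plainly applies.

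**On withdrawn subjects.** Section 6.4.1 retains those who ask to discontinue, and for them Visit 4 is part of follow-up. Those who are lost or refuse contact would not be reached by another call. Section 8.1.3 already captures an SAE that causes withdrawal, 7.1 lets a subject who becomes pregnant after vaccination remain for safety monitoring, and withdrawal on eligibility grounds is discretionary. All of this stands and makes the affected group small. It does not close the gap. Documenting an outcome and following unresolved AEs, as 6.4.2 asks, is not a scheduled enquiry about new SAEs and NDCMCs to Month 12.

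**On size.** The 10% in the illustration is the protocol's allowance for evaluable subjects (3.3), not a rate of investigator- or sponsor-initiated withdrawal. A reader might take 0.77 points as a ceiling, but excluding the affected subjects gives 1.41 on the same inputs. No upper bound should be claimed.

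**Conclusion.** The point holds as a minor one, in two separate parts.

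First, the related-only floor in 8.1.4.1 starts too early because 8.1.4 gives SAEs the same end date as nonserious AEs. It is inconsistent with 8.1, 8.1.4 (second sentence) and 8.4.1. It is not an instruction to withhold unrelated SAEs, and subjects still in follow-up lose no endpoint data. Section 8.1.4.2 is incomplete rather than contradictory.

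Second, the follow-up that 6.4 specifies stops at Month 6 for Stage 2 subjects withdrawn by the investigator or sponsor, short of a 12-month primary endpoint. It would be wrong to read this as loss of 12-month follow-up for every Stage 2 subject who stops early.

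The numerical effect is probably small beside sampling error. With 1% affected and the other assumptions above, it is below 0.1 points if partly followed subjects are kept, and 0.01 × (0.2213 − 0.08) = 0.14 points at HR 3 if they are excluded. The interval at 18/220 is several points wide on either side. That judgement rests on assumed rates, and neither the size nor the direction can be fixed from the documents. The wording findings depend on none of these assumptions.

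**What to change.** 1. In 8.1.4, define two periods: nonserious AEs from consent through Visit 2, and SAEs and NDCMCs from consent through Visit 3 (Stage 1) or Visit 4 (Stage 2). Tie 8.1.4.1 to the second period, so that its awareness and related-only sentence applies only after the last visit. Have 8.1.4.2 refer to the same two periods, in line with 8.1.
2. In 6.4, add a 12-month safety contact for withdrawn Stage 2 subjects unless consent for contact is withdrawn, and cross-refer to 6.4.1. The cross-reference is useful because 6.4 lists unwillingness to continue among its withdrawal reasons without pointing to the rule that keeps such subjects in follow-up.

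The cost is wording in four sections and a small number of telephone calls. For scale, each 1% of the 440 Stage 2 subjects is about 4 calls (0.01 × 440 = 4.4). No analysis or sample size changes.
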